9.2 SAMPLE SIZE DETERMINATION

With 280 participants and 20% loss to follow-up, we will have 75 evaluable participants in each treatment group. Based on published literature (*Kroenke K et. al JAMA July 2014*), the estimated standard deviation (SD) for BPI GPS score is 2.2. Assuming a moderate correlation of 0.5 between baseline and follow-up measures, we estimate that the SD in an analysis of covariance (ANCOVA) will be approximately 1.9. Therefore, we will have 90% power to detect a difference of -1 in BPI GPS score between combination groups (n= 150) and drug only group (n=75) for Aim 1. The power will be 83% power for comparison between combination with health care professional (n=75) and combination without health care professional (n=75) for Aim 2. All power calculations are based on two-sided t tests with alpha level of 0.025 to adjust for Bonferroni correction of testing two main hypotheses.

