9.4.2 ANALYSIS OF THE PRIMARY ENDPOINT(S)

Primary Outcome

The primary outcome of the study is BPI GPS score collected at Weeks 13 and 25. BPI GPS is a self-report measure of pain severity and interference with proven reliability and validity across different pain conditions. The overall score is defined as the average of 11 items. Two subscales are also defined: BPI pain severity and BPI pain interference. BPI pain severity is the average of 4 items asking about current pain and worse, least, and average pain in the past week. BPI pain interference is the average of 7 items that rate how pain interferes with various activities (higher score indicate greater pain interference). All study participants will be analyzed according to randomized treatment assignment regardless of adherence to the treatment protocols. We have two primary hypotheses (H1 and H2):

H1: Combination treatment with and without health care professional support is more effective than duloxetine monotherapy in improving BPI GPS.

H2: Combination treatment with health care professional support is more effective than combination treatment without health care professional support in improving BPI GPS.

Research has shown that the use of ANCOVA with baseline measure as a covariate is an optimal method in both design and analysis of trials with a continuous primary outcome. Compared to the use of change score as the primary outcome, ANCOVA is generally superior in terms of efficiency, precision, and power. Therefore, the primary analysis will be Week 13 and 25 BPI scores as a primary outcome while adjusting for baseline measurement.

In primary analysis, we will fit a LMM to account for the correlation among the repeated measures. The model will include indicator variables for intervention arms, visit, and the interaction term. Covariates will include the pre-randomized measure of BPI global score, the stratification factor opioid use, and the number of pain sites. Average follow-up BPI global pain scores for the 3 intervention groups will be estimated using least square means. Two different contrasts will be constructed to test H1 and H2 separately, each at the significance level of 0.025.

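### Section 9.2's 90% power for H1 does not follow from its own inputs, which give about 93%; the section also leaves open which follow-up score the difference of -1 refers to

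*Combined protocol and SAP*

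**What the plan says.** Section 9.2 starts from 280 participants and 20% loss, giving 75 evaluable per arm, and takes an SD of 2.2 for BPI GPS from a published trial. The adjustment for baseline rests on this premise: "Assuming a moderate correlation of 0.5 between baseline and follow-up measures". The resulting SD is then given in these words: "we estimate that the SD in an analysis of covariance (ANCOVA) will be approximately 1.9". For Aim 1 (150 vs 75) it states that "we will have 90% power to detect a difference of -1 in BPI GPS score between combination groups" and the drug-only group. For Aim 2: "The power will be 83% power for comparison between combination with health care professional (n=75) and combination without health care professional (n=75"). On method: "All power calculations are based on two-sided t tests with alpha level of 0.025", the split allowing for two main hypotheses. No visit is named for the -1, and no correlation between the two follow-up visits is given.

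Section 9.4.2 says that "the primary analysis will be Week 13 and 25 BPI scores as a primary outcome while adjusting for baseline measurement". It fits a linear mixed model with arm, visit and their interaction, and then: "Average follow-up BPI global pain scores for the 3 intervention groups will be estimated using least square means". H1 and H2 are each tested by one contrast at 0.025.

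**The concern.** There are two separate matters.

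- **Reproducibility.** Section 9.2 supplies every input needed to check both power figures. They share the SD, the difference, the alpha and the test, and differ only in group sizes. One set of inputs should therefore give both figures. If it does not, one of them is wrong or rests on an input that is not shown.
- **Quantity powered.** The SD used belongs to one follow-up score, whereas the planned contrasts concern scores averaged over two visits. The reader cannot tell whether -1 is meant at Week 13, at Week 25, or on average.

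These are the only power statements for the two primary hypotheses. Anyone who judges the precision of the contrasts, or interprets a null result for H2, will rely on them.

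**Working it through.** **Inputs, all from Section 9.2.** Difference 1 (absolute value); SD 2.2; baseline to follow-up correlation 0.5; ANCOVA SD about 1.9; groups of 150 vs 75 (H1) and 75 vs 75 (H2); two-sided t test, alpha 0.025.

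**Step 1: the SD.** 2.2 × sqrt(1 − 0.5²) = 2.2 × 0.866 = 1.905, which the plan rounds to 1.9. This is the residual SD of one follow-up score after adjustment for baseline.

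**Step 2: reproduce the stated power.** Noncentrality = difference / (SD × sqrt(1/n1 + 1/n2)), with df = n1 + n2 − 2 and power from the noncentral t.

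- H2: 1 / (1.9 × sqrt(1/75 + 1/75)) = 1 / (1.9 × 0.1633) = 3.223; df 148. Power 83.0%, as stated.
- H1: 1 / (1.9 × sqrt(1/150 + 1/75)) = 1 / (1.9 × 0.1414) = 3.722; df 223. Power 92.8%, against the stated 90%.

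The agreement on H2 shows that this is the plan's method.

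**Step 3: can rounding or another choice explain 90%?**

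| Change | H1 | H2 |
|---|---|---|
| Unrounded SD 1.905 | 92.6% | 82.8% |
| 280 × 0.8 / 3 = 74.67 per arm | 92.7% | 82.8% |
| Alpha 0.05 | 96.0% | 89.3% |
| Alpha 0.0125 | 88.5% | 75.5% |
| SD 2.2 (no ANCOVA gain) | 83.0% | 69.8% |

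None gives 90% and 83% together.

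**Step 4: force H1 to 90% by moving one input.** This takes an SD of 1.996, or a difference of 0.952, or 68.05 per arm. In each case H2 becomes 78.8%.

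**Step 5: the two-visit average.** Let r be the correlation between the Week 13 and Week 25 scores. The documents do not give it, so a range is assumed. Take SD 2.2 and baseline correlation 0.5 at both visits, equal visit weights, and 75 per arm observed at both. The average then has variance 2.2² × (1 + r)/2, and adjustment for baseline removes 2.2² × 0.25. The residual SD is therefore 2.2 × sqrt((1 + r)/2 − 0.25).

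| r | Residual SD | H1, average −1 | H2, average −1 |
|---|---|---|---|
| 0.5 | 1.556 | 98.9% | 95.2% |
| 0.7 | 1.704 | 97.0% | 90.7% |
| 0.9 | 1.841 | 94.3% | 85.5% |
| 1.0 | 1.905 | 92.6% | 82.8% |

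At r = 1 the second visit adds nothing and the single-score figures (unrounded SD) return.

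**Step 6: dependence on what -1 means.** If the difference were -1 at one visit and -0.5 at the other, the average would be -0.75. With r = 0.7, power is then 80.3% for H1 and 66.7% for H2, both below the stated figures.

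**The case against.** The best defence of the 90% is that it is a conventional target which the inputs meet, so it may mean at least 90%. The error is on the safe side, and H2, the comparison with less power, reproduces exactly. That limits the consequence but does not remove the mismatch: the text does not say at least, and its next sentence gives H2 to the percentage point. The figure could also be left over from another sample size. Section 9.3 mentions a target of 250, and 250 × 0.8 / 3 = 66.7 per arm gives 89.3% for H1, but 77.9% for H2. The documents do not state this origin, so it remains a guess.

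On the SD, the plan openly bases its power on t tests with an ANCOVA SD. Sizing a repeated-measures trial on a single follow-up score is common and avoids guessing a visit correlation. This stands. Using the single-score SD is an acceptable simplification and does not contradict Section 9.4.2. What remains open is which score or average the -1 describes. Section 9.4.2 does not write out contrast coefficients either; averaging the two visits equally is the natural reading of its wording.

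A reader might infer that the stated figures are simply conservative because a second visit adds information. The documents do not support that without a condition. It holds only if the difference averaged over both visits is -1, and there are reasons why the effect may differ between visits. Three of the six support calls (Weeks 14, 18 and 22) come after Week 13, per Section 6.1.1. Section 2.2 reports that between-group differences shrank at follow-up in a cited web-based CBT trial.

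**Conclusion.** The H1 power in Section 9.2 is misstated: its own inputs give 92.8% (92.6% unrounded), not 90%, and no single change to the SD, difference or arm size reconciles it with 83% for H2. This rests only on figures in Section 9.2. Separately, the section does not define the -1 in terms of the averaged score that is tested.

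Both points are minor. At an averaged difference of -1, under the equal-variance, complete-data assumptions in the working, power is at least 92.6% for H1 and 82.8% for H2 for any visit correlation up to 1, so the sample size is not undermined. A reader might instead infer that the trial is underpowered; nothing in Section 9.2's own assumptions supports that. The lower figures of about 80% and 67% come from an illustrative smaller averaged effect (-0.75, correlation 0.7) and are not a prediction.

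**What to change.** In Section 9.2:

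1. Restate H1 power as about 93%, or give the inputs that yield 90% and restate H2 from those same inputs.
2. Keep the single-score figures as the basis, and state that the -1 is the difference averaged over Weeks 13 and 25.
3. Optionally, add power for the two-visit average, with the visit correlation marked as an assumption running from 0.5 to 1.0: 98.9% down to 92.6% for H1, and 95.2% down to 82.8% for H2. Note beside it that this is at or above the single-score power only if the averaged difference is -1, and that an average of -0.75 with correlation 0.7 gives about 80% and 67%.

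The cost is one corrected figure and one or two sentences. Sample size, endpoint, visits, model and data collection do not change.

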9.3 POPULATIONS FOR ANALYSES

WF Baptist Health. We have identified 9,243 unique individuals in the age range of at least 18 years old or older; seen at the primary care clinic over the past 12 months; and who received one of the relevant ICD 10 codes. The pool of potentially eligible participants (N=9,243) is large enough to get us to our target sample size of 250 at WF Baptist Health. This pool of 9,243 individuals has the following characteristics: Gender: 62% females and 38% males; Race: 21% African Americans, 2.8% Hispanics, 1% Asians and 72.2% Whites. Over the past 4 months we surveyed 86 patients with CMP (48% females; mean age= 51 years old) who were seen in one of WF Baptist Health primary care centers. We found that 58 (67%) patients continue to have a significant amount of pain despite current treatments, and also reported that pain prevented them from working or doing the things they enjoy almost every day. From these 58 patients, 50 (86%) have expressed willingness to participate in clinical studies to help reduce their pain and improve their quality of life.

9.4 STATISTICAL ANALYSES

9.4.1 GENERAL APPROACH

See the following sections for details.

9.4.2 ANALYSIS OF THE PRIMARY ENDPOINT(S)

Primary Outcome

The primary outcome of the study is BPI GPS score collected at Weeks 13 and 25. BPI GPS is a self-report measure of pain severity and interference with proven reliability and validity across different pain conditions. The overall score is defined as the average of 11 items. Two subscales are also defined: BPI pain severity and BPI pain interference. BPI pain severity is the average of 4 items asking about current pain and worse, least, and average pain in the past week. BPI pain interference is the average of 7 items that rate how pain interferes with various activities (higher score indicate greater pain interference). All study participants will be analyzed according to randomized treatment assignment regardless of adherence to the treatment protocols. We have two primary hypotheses (H1 and H2):

H1: Combination treatment with and without health care professional support is more effective than duloxetine monotherapy in improving BPI GPS.

H2: Combination treatment with health care professional support is more effective than combination treatment without health care professional support in improving BPI GPS.

Research has shown that the use of ANCOVA with baseline measure as a covariate is an optimal method in both design and analysis of trials with a continuous primary outcome. Compared to the use of change score as the primary outcome, ANCOVA is generally superior in terms of efficiency, precision, and power. Therefore, the primary analysis will be Week 13 and 25 BPI scores as a primary outcome while adjusting for baseline measurement.

In primary analysis, we will fit a LMM to account for the correlation among the repeated measures. The model will include indicator variables for intervention arms, visit, and the interaction term. Covariates will include the pre-randomized measure of BPI global score, the stratification factor opioid use, and the number of pain sites. Average follow-up BPI global pain scores for the 3 intervention groups will be estimated using least square means. Two different contrasts will be constructed to test H1 and H2 separately, each at the significance level of 0.025.

We will conduct several sensitivity analyses to evaluate the robustness of the results. First, we will use inverse probability weighting (IPW) to account for missing data. We will identify the baseline characteristics that may be associated with lost to follow-up and derive weights for use in IPW analysis. Additional sensitivity analysis will include indicators of new pain related medication taken, and any use of complementary treatment.

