1.3 SCHEDULE OF ACTIVITIES

Table 1. Study Measures and Time Points for Data Collection in PRECICE

Telephone Contacts/Visits ^a	Pre-Screening Visit	Week 0	Week 1	Week 2	Week 3	Week 4	Week 6	Week 10	Week 13	Week 14	Week 18	Week 22	Week 25	PRN
Type of Contact/Visit ^{b,c}	TC	IPV	IPV	TC	TC	TC	TC	TC	IPV	TC	TC	TC	IPV	PRN
Screening														
Phone Pre-Screening	✓													
Randomization			✓											
Physical Measures														
Blood Pressure	✓	✓							✓				✓	
Height	✓												✓	
Weight	✓												✓	
Urine Pregnancy Test	✓								✓					
Questionnaires														
3-item Pain Intensity Interview	✓								✓				✓	
Compiled Questionnaires		✓							✓				✓	
o Brief Pain Inventory														
o Generalized Anxiety Disorder (GAD-7)														
o Patient Health Questionnaire (PHQ8)														
o Global Rating of Change (GRoC)														
o Pain Catastrophizing Scale (PCS)														
o PROMIS Adult Self-Report														
o Chronic Pain Coping Inventory (CPCI)														
Demographics with Medical Diagnosis		✓												
Informed Consent		✓												
Missed Visit Form													✓	
Modified Pain Detect	✓													
Non-study Medication List	✓								✓				✓	
Nurse Counselling Tracking Form						✓		✓	✓		✓	✓	✓	
Opioid Risk Tool	✓													
Participant Status													✓	
Serious Adverse Event Report Form													✓	
Study Drug Accountability Log	✓ ^d	✓ ^e								✓			✓ ^f	
Study Medication Modification				✓						✓			✓ ^g	
Study Medication Symptom Monitoring Form		✓ ^h	✓ ⁱ			✓ ⁱ			✓ ⁱ		✓		✓ ^j	
TAPS – Tobacco, Alcohol, Prescription	✓												✓	
EMR Health Care Utilization ^h														

^a Weeks with participant contact are listed on this table.

^b IPV indicates in-person visit.

^c TC indicates telephone contact.

^d At study entry, all participants will receive duloxetine 30 mg once daily for one week.

^e At week 1, participants will receive duloxetine 60 mg once daily for 24 weeks.

^f At week 25, all participants will be provided duloxetine 30 mg once daily for 7 days and medication treatment will then stop (tapering regimen).

^g Phone administration on as needed basis only if participant calls the research office and complains of a potential side effect.

^h EMR Health Care Utilization will be collected at one year after randomization.

ⁱ Option of using text messaging as an adjunct to phone calls to assess duloxetine symptoms monitoring at weeks 2 and 4.

Revised 07/19/2021

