Pain-related appraisals and beliefs about pain can affect an individual's affective and behavioral response to pain^{27,28}. People are less able to adjust to pain when they believe that pain is a signal of damage, activity should be avoided when one has pain, pain leads to disability, pain is uncontrollable, and pain is a permanent condition ^{27,29}. For example, patients with low back pain believed that a wrong movement could have serious negative consequences for their back ². Moreover, this belief was

associated with reduced activity levels and increased disability. Among patients with fibromyalgia, positive outcomes were most closely related to: (1) an increased sense of control over pain, (2) a belief that one is not necessarily disabled by pain, and (3) a belief that pain is not necessarily a sign of damage³⁰.

One pain-related appraisal, catastrophizing (defined as an exaggerated negative orientation toward actual or anticipated pain experience and effects), has been an important therapeutic target in managing chronic pain³¹⁻³³.

Pain coping. Coping is the use of behavioral and cognitive techniques to manage demands perceived as stressful³⁴. Variations in pain coping are significantly related to pain, physical function and pain behavior³⁵⁻³⁷. Both active and passive coping dimensions are significantly related to chronic pain adjustment³⁸. In patients with osteoarthritis, greater self-control and increased rational thinking were associated with lower pain ratings and less self-reported physical disability³⁹. Among chronic pain patients, both poor coping skills and maladaptive pain related beliefs predicted physical disability²⁷. These findings suggest the importance of targeting specific pain-related beliefs and coping strategies for modification to reduce physical disability.

Cognitive Behavioral Therapy (CBT)

Modification of cognition (pain-related appraisals and beliefs) and behavior can positively or negatively affect the course of an individual's chronic pain condition. The goal of CBT is to aid the patient in re-conceptualizing his or her personal view of pain and role (from passive to a more proactive role) in the process of healing. CBT is effective in the management of low back pain, neck pain, temporomandibular joint pain, knee osteoarthritis, and fibromyalgia⁴⁰.

Scientific Premise

i. Optimizing Treatment Outcome: Combining Duloxetine and CBT

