6.3 MEASURES TO MINIMIZE BIAS: RANDOMIZATION AND BLINDING

The PI and the analysis team at the clinical site will remain blinded to group assignment throughout the study. Randomization will be stratified by number of pain sites (≤ 2 vs. ≥ 3 sites) and opioid use. Number of pain sites is included as a stratification variable, since it has been associated with worse outcomes ⁸¹⁻⁸³.

The data team , who is blinded of treatment group assignment, has the primary responsibility of analyzing outcome data throughout the study.

Randomization will be accomplished through the REDCap Randomization Module. REDCap helps implement a defined randomization model within the study project, by allowing users to 1) Define all of the randomization parameters; 2) Create and upload a custom randomization table (i.e., allocation list). The table serves as a lookup table for deciding how to randomize subjects/records. The module also monitors the overall allocation progress and assignment of randomized subjects.

For more randomization details, see MOP chapter 07, Randomization.

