9.4.7 SUB-GROUP ANALYSES

Subgroup Analyses

We will conduct subgroup analysis using LMMs to test the interactions between intervention arm (with and without health care professional support vs. monotherapy) and baseline characteristics. The subgroups include comorbid psychological distress, use of opioid, and number of painful body sites (dichotomized at the median value). The interaction will be tested at the 0.10 level of significance. A significant interaction is indicative of potential moderating effect of baseline characteristic such as psychological distress for predicting the mean BPI GPS score under combination therapy.

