- p. Physical Medicine/Rehabilitation (PMR)
- q. Rheumatology
- r. Integrative Medicine
- s. Psychiatry
 - i. Medication
 - ii. Counseling
 - iii. Medication + counseling
- t. Quartet system for PCP – psychiatry/psychology referral (not currently link with Wake One)
- u. Physical therapy
- v. Occupational therapy

7.3 Number of orthopedic or musculoskeletal surgeries from enrollment date to the one-year anniversary. See attached relevant CPT codes.

8 *PHQ-ADS* is a composite of PHQ-8 and GAD-7 scores. PHQ-ADS is a single measure for assessing psychological distress in clinical practice and research ⁷⁸. This is especially salient given the frequent co-occurrence of depression and anxiety. PHQ-ADS cut points of 10, 20 and 30 were shown to represent mild, moderate, and severe levels of psychological distress, respectively. We are using cut point of ≥ 20 to represent moderate level of psychological distress.

9 *Frequency of Practicing Pain Coping Skills*. During the outcome data collection at weeks 13 and 25 we will ask participants how many days they practiced pain coping skills in the past 2 weeks (maximum of 14)³.

10 *Others*. The study will track medication use but will not control or restrict medication use as part of the study. To assess co-intervention effect, a treatment survey will inquire about specific treatments the patient has received (opiates and other analgesics, psychotropic medications and use of complementary and integrative health modalities such as acupuncture) for pain since the last follow-up ⁶⁹.

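### The primary mixed model is valid as written, but it could cheaply gain some precision by adjusting for baseline PHQ-ADS and Pain Catastrophizing Scale scores, which are collected before randomization

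*Combined protocol and SAP*

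**What the plan says.** - **Primary model (9.4.2).** The linear mixed model contains arm, visit and their interaction. On adjustment it says: "Covariates will include the pre-randomized measure of BPI global score, the stratification factor opioid use, and the number of pain sites". The same section argues for ANCOVA over change scores on grounds of efficiency, precision and power.
- **Stratification (6.3).** "Randomization will be stratified by number of pain sites" and by opioid use. Number of pain sites is the one variable given an explicit prognostic reason, "since it has been associated with worse outcomes", and it is in the model.
- **Timing (1.3, Table 1).** The compiled questionnaires are completed at Weeks 0, 13 and 25 and include the PHQ-8 and the entries that begin "Generalized Anxiety Disorder (GAD-7" and "Pain Catastrophizing Scale (PCS". Randomization is at Week 1, so the Week 0 values are true pre-randomization covariates.
- **Distress measure (9.4.9).** PHQ-ADS is the composite of PHQ-8 and GAD-7: "PHQ-ADS is a single measure for assessing psychological distress in clinical practice and research".
- **Role of these variables.** Section 2.2 presents catastrophizing as a therapeutic target and reports: "Among chronic pain patients, both poor coping skills and maladaptive pain related beliefs predicted physical disability". It also describes change in catastrophizing as a mediator of the CBT effect. Section 9.4.7 tests distress as an effect modifier, looking for a "moderating effect of baseline characteristic such as psychological distress for predicting the mean BPI GPS score under combination therapy".
- **Other baseline characteristics** enter only through the inverse-probability-weighting sensitivity analysis in 9.4.2, and they are still to be identified.

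**The concern.** The plan's efficiency argument for adjusting on baseline BPI extends to any other pre-randomization variable that is related to outcome. The protocol gives reasons to expect such a relation here. Pain-related beliefs are reported to predict disability, and pain interference is one of the two components of BPI GPS. Distress already has its own exploratory hypothesis (9.1) and subgroup test (9.4.7). The scores will be in the database whether or not they are used.

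Three things are at stake, all modest:

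1. Precision, chiefly for H2, which has the lower stated power (83%).
2. Chance imbalance in distress or catastrophizing, on which randomization is not stratified.
3. The missing-at-random assumption of the mixed model when 20% loss is planned for. That assumption conditions only on what is in the model.

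**Working it through.** **Inputs from 9.2.** SD of BPI GPS 2.2; baseline to follow-up correlation 0.5; ANCOVA SD about 1.9; difference 1 point; two-sided alpha 0.025 per hypothesis; 280 randomized, 20% loss, 75 evaluable per arm.

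**Reproducing the plan's figures.**
- ANCOVA SD = 2.2 × √(1 − 0.5²) = 1.905, stated as about 1.9.
- Evaluable per arm = 280 × 0.8 / 3 = 74.7, stated as 75.
- H2, two-sample t test, 75 vs 75, SD 1.9: power 83.0%, stated as 83%.
- H1, 150 vs 75, SD 1.9: power 92.8%, stated as 90%. The stated figure is conservative and does not bear on this point.

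**Effect of the added covariates (single time point).** Let x be the share of ANCOVA residual variance that baseline PHQ-ADS and PCS explain beyond baseline BPI. The documents do not give x, so the values below are assumptions. Residual SD = 1.9 × √(1 − x), with two fewer degrees of freedom. The equivalent gain in sample size is 1/(1 − x) − 1.

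| x | Residual SD | H2 power | H1 power | Equivalent extra participants |
|---|---|---|---|---|
| 0 | 1.900 | 83.0% | 92.8% | 0% |
| 2% | 1.881 | 83.8% | 93.3% | 2% |
| 5% | 1.852 | 85.0% | 94.0% | 5% |
| 10% | 1.802 | 87.0% | 95.1% | 11% |

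If x = 0, the two lost degrees of freedom cost about 0.01 percentage point of H2 power (83.00% to 82.99%).

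**If the contrast averages Weeks 13 and 25.** Section 9.4.2 estimates average follow-up scores by arm. Keep SD 2.2 and baseline correlation 0.5 at each visit, and assume a between-visit correlation r, which is not in the documents. The adjusted SD of the average is 2.2 × √((1 + r)/2 − 0.25).

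| r | SD | H2 power, x = 0 | H2 power, x = 5% |
|---|---|---|---|
| 0.5 | 1.556 | 95.2% | 96.1% |
| 0.6 | 1.632 | 93.1% | 94.3% |
| 0.7 | 1.704 | 90.7% | 92.1% |
| 0.8 | 1.774 | 88.1% | 89.8% |

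The 5% case then adds about 0.9 to 1.7 points.

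**Does the omission bias anything?** A simulation used 4,000 runs per scenario, 75 vs 75, with an omitted covariate explaining 5% of residual variance. Without the covariate, the mean estimate was −0.997 for a true −1 and the rejection rate under the null was 0.022 against a nominal 0.025. Power was 0.82 without the covariate and 0.84 with it. The omission costs a little precision. It does not bias the estimate or inflate the type I error.

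**Chance imbalance.** With 75 per arm, the standardized baseline difference between two arms has SD √(2/75) = 0.163. A gap above 0.3 SD in one given variable has probability of about 7%. If that variable explains 5% of residual variance (assumed), a 0.3 SD gap moves the estimate by 0.3 × √0.05 × 1.9 = 0.13 points, or 13% of the 1-point target.

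**The case against.** The strongest case against is that nothing here is broken. The model adjusts for the baseline outcome and both stratification factors. Leaving a prognostic covariate out of a linear model in a randomized comparison biases neither the estimate nor the test, and the stated power is met without it. Chance imbalance is already allowed for in the standard error. All of this stands.

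A reader might infer that the protocol itself treats distress and catastrophizing as drivers of outcome, so that the model contradicts its own rationale. The documents do not support that. Distress is given the role of moderator, and 9.4.7 already tests it as one. Change in catastrophizing is given the role of mediator. The sentence on coping and beliefs concerns physical disability. It does not concern PHQ-ADS, and it does not say that PCS predicts follow-up BPI GPS. The mediation statement is no reason against adjustment either, because the covariate would be the Week 0 score and not its change.

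The increment may also be small. Baseline BPI interference includes mood, enjoyment of life and sleep (section 3), so it may already carry part of the distress information. The 83% starting point is a single-time-point figure, and averaging two visits would leave less to gain. Finally, other baseline variables could be proposed on similar grounds. These points limit the size and priority of the recommendation. They do not show a material cost to adopting it.

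**Conclusion.** This is an optional, low-cost improvement to a sound primary model. The expected benefit for H2 is 0.8, 2.0 or 4.0 points of power at an assumed 2%, 5% or 10% of residual variance on the protocol's single-time-point basis. If the contrast averages the two visits, the 5% case gives about 1 to 2 points. Each figure rests on a share of variance that the documents do not supply, and the true increment could be zero.

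The further benefits are qualitative: protection against chance imbalance in distress, and a more plausible missing-at-random assumption if distress or catastrophizing predicts both dropout and pain. It would be wrong to conclude that the primary analysis is biased, that its type I error is inflated, or that H2 misses its stated power without these covariates.

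**What to change.** In 9.4.2 and 9.4.3, add baseline PHQ-ADS and PCS total scores, both continuous, as fixed covariates in the primary and secondary mixed models. Make the change before any outcome data are seen by arm, because a later addition would look data-driven. State a simple rule for missing baseline scores, for example single mean imputation of the covariate without regard to arm, so that no randomized participant is dropped. Keep the present model as a pre-specified sensitivity analysis.

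The cost is a few sentences of analysis-plan text and about two degrees of freedom. No new data, visits or participant burden are involved.
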